2.0 OBJECTIVES & ENDPOINTS

2.1 Primary Objective & Endpoint

To assess the difference in percentage of participants who develop a grade 2 or greater rash in the control group as compared to the case group of preemptive treatment with topical steroids (triamcinolone 0.1% cream for application to face, chest and back) when administered concomitantly for 6 weeks with erlotinib, cetuximab, panitumumab, afatinib or osimertinib to prevent papulopustular eruptions.

2.2 Secondary Objectives & Endpoints

- 2.2.1 To assess the difference in maximum severity of rash between the preemptive treatment group and the reactive treatment group.
- 2.2.2 To assess the difference in change in quality-of-life due to rash between the two treatment groups.
- 2.2.3 To determine whether there is a difference in adherence to chemotherapy between the two treatment groups.
- 2.2.4 To determine if the results of baseline nasal swab cultures are associated with rash development or rash severity.

3.0 PATIENT ELIGIBILITY

The target population for this study is patients with a histologically or cytologically confirmed cancer diagnosis for which EGFRI treatment is indicated. This will be single-center trial conducted at the Robert H. Lurie Cancer Center of Northwestern University.

A total of 84 subjects will be needed for this trial. Approximately 10 potentially eligible patients are seen per month, and it is anticipated that at least 4 per month will be accrued. Potential patients may be referred to the Principal Investigator (PI) at Northwestern University, [name] at [contact].

Eligibility will be evaluated by the study team according to the following criteria. Eligibility waivers are not permitted. Subjects must meet all of the inclusion and none of the exclusion criteria to be registered to the study. Study treatment may not begin until a subject is registered. Please refer to Section 11 for complete instructions regarding registration procedures.

3.1 Inclusion Criteria

- 3.1.1 Patients must have a histologically or cytologically confirmed cancer diagnosis for which EGFRI treatment is indicated
- 3.1.2 Initiation of topical steroids or control treatment within 7 days of initiation of cetuximab, erlotinib, panitumumab, afatinib or osimertinib
- 3.1.3 Patients must be age \geq 18 years.
- 3.1.4 Life expectancy of greater than 6 weeks
- 3.1.5 Patient able to use topical medications reliably and complete questionnaires with assistance if needed
- 3.1.6 Patients must have the ability to understand and the willingness to sign a written informed consent prior to registration on study.

3.2 Exclusion Criteria

- 3.2.1 Patients who have used systemic or topical steroids within 7 days of trial registration, or start systemic or topical steroids for reasons unrelated to trial during the 6-week follow up period. Systemic steroids as part of chemotherapy regimen are allowed.
- 3.2.2 Patients who have used antibiotics within 7 days of trial registration, or start antibiotics for other conditions during the 6-week follow up period
- 3.2.3 History of allergic reactions to topical steroids
- 3.2.4 Patients with any rash at the time of study registration
- 3.2.5 Uncontrolled intercurrent illness including, but not limited to, ongoing or active infection, symptomatic congestive heart failure, unstable angina pectoris, cardiac arrhythmia, or psychiatric illness/social situations that would limit compliance with study requirements.

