4.0 TREATMENT PLAN

4.1 Overview

The treatment in this study will include a twice daily application of 0.1% triamcinolone topical cream, applied to the face, chest, and back. In addition, all patients will be instructed to adhere to the same skin treatment regimen, regardless of whether they are in the preemptive or control arm, which will be administered beginning day -3 to day 7(three days before the administration of the first EGFRI dose until 7 days after the administration of the first EGFRI dose) and will be continued through week 6. This regimen will include daily moisturizers as well as use of broad spectrum sun protection before going outdoors.

Patients will be followed every 2 weeks for 6 weeks total, and at each visit will fill out a FACT-EGFRI-18 questionnaire. Optional nasal swab cultures to check for bacterial and fungal growth will be taken at the first and last visit, in addition to any time a culture of the skin is taken. If the patient agrees to the culture and there is bacterial colonization, they will be treated as standard of care. Standard of care is not to treat a positive nasal swab. If an infection develops, this will be treated with antibiotics that cover the bacteria isolated in the culture. In addition, standardized photographs will be taken at each visit, and graded by two blinded dermatologists, if any rash appears. These photos may be used in the future for academic purposes. If they are used outside of the study, the eyes of the participants will be blacked out to help maintain confidentiality. Patients will be given the option to conduct the visits in-person or remotely. If the visit will be conducted remotely, then all required study documentation, diaries, questionnaires, and photography will be submitted to the study team prior to the remote visit for review. For remote visits, the study coordinator will call the subject at the appointment time to review the protocol, answer questions, and review diaries, questionnaires, and AEs.

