4.6 Duration of Follow Up

Patients will be enrolled in the study for 6 weeks. They will be followed in clinic every 2 weeks with the option for remote visits instead of in-person visits by submitting the required documentation and photography to the study team ahead of the remote visit for review. The

NU Study Number: JNC06142016 Other Study Numbers: STU00203631; NU 16D05

remote visit will happen using telephone to review the protocol, answer questions and concerns, and review diaries, questionnaires, and AEs.

They will not be followed up after the final visit during the 6th week, when they will terminate the drug regimen.

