4.7 Removal of Subjects from Study Treatment and/or Study as a Whole

Patients can be taken off the study treatment and/or study as a whole at any time at their own request, or they may be withdrawn at the discretion of the investigator for safety, behavioral or administrative reasons. The reason(s) for discontinuation must be clearly documented on the appropriate eCRF and may include:

NU Study Number: JNC06142016 Other Study Numbers: STU00203631; NU 16D05

- Patient voluntarily withdraws from treatment (follow-up permitted)
- Patient withdraws consent (no follow-up permitted)
- Patient is unable to comply with protocol requirements
- Patient demonstrates disease progression
- Patient experiences unacceptable toxicity as determined by either the patient's physician or by the patient himself
- Treating physician determines that continuation on the study would not be in the patient's best interest
- Patient becomes pregnant
- Patient develops a second malignancy that requires treatment which would interfere with this study
- Patient becomes lost to follow-up (LTF)

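### Sections 3.2.1 and 3.2.2 list steroid or antibiotic starts during follow-up as exclusion criteria, and nothing says that these randomised patients stay in the primary analysis

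*Combined protocol and SAP*

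**What the plan says.** Section 3.2.1 excludes recent steroid users and adds those who later start: "or start systemic or topical steroids for reasons unrelated to trial during the 6-week follow up period". It carves out one case: "Systemic steroids as part of chemotherapy regimen are allowed". Section 3.2.2 does the same for antibiotics: "or start antibiotics for other conditions during the 6-week follow up period".

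Section 3.0 ties the criteria to entry. A patient must meet none "of the exclusion criteria to be registered to the study", and it adds that "Eligibility waivers are not permitted".

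On what follows entry, 4.1 says "Patients will be followed every 2 weeks for 6 weeks total" and 4.6 says "Patients will be enrolled in the study for 6 weeks". Neither makes an exception. Section 4.7 lists possible reasons for removal. Steroid or antibiotic starts are not named, but the list is open and patients can be taken off because "they may be withdrawn at the discretion of the investigator for safety, behavioral or administrative reasons".

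Continued follow-up is stated expressly for two other groups: patients taken off the cream for side effects (4.3), and patients treated for rash (study schema and 4.5). The only statement on who is evaluable (4.3) concerns toxicity. Section 9.3 gives the Mantel-Haenszel test and the odds ratio without saying which patients enter them. The 3% allowance in 9.2 is for loss to follow-up.

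**The concern.** An exclusion criterion that depends on something happening after randomisation can act only on patients already in the trial. If it is used to drop them, the two analysed groups are no longer the randomised groups.

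Three features make this more than a formality:

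- **Known allocation.** The control arm receives no preemptive treatment (4.2.1) and no placebo is described. Photographs are graded by blinded dermatologists (4.1), but no passage blinds whoever decides that a start was unrelated to the trial or for another condition.
- **A link to the outcome.** Steroids and antibiotics are also used to treat the rash (4.5), so deciding why a drug was started can be close to deciding whether the patient had the endpoint.
- **No scheduled record.** The medication list belongs to the baseline history (5.0, footnote 1). The diary columns in Appendix 2 cover application, rash and symptoms. Under 7.2.1, adverse events are collected only if at least possibly related to the cream; serious events are the exception (7.2.3).

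An analyst could cite 3.2 to drop such patients, or 4.1 and 4.6 to keep them, and could choose after seeing the data. Removal that depended on both arm and rash would bias the odds ratio, and any removal would shrink the analysed sample.

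**Working it through.** **Inputs.** From 9.2: rash in 45% (steroid) and 75% (control), 42 per arm, 80% power, 3% loss. From the Study Summary: two-sided 5%. Assumed, because the documents give no rate of such starts: 5% or 10% of patients affected.

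**1. The plan's own figure.** For two proportions, with pooled variance under the null and no continuity correction:

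n per arm = [1.96 × √(2 × 0.60 × 0.40) + 0.842 × √(0.45 × 0.55 + 0.75 × 0.25)]² / 0.30² = 40.7, so 41.

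Power is 79.3% at 40 per arm and 81.3% at 42. After 3% loss, 42 × 0.97 = 40.74 per arm gives 80.1%. The stated 80% is reproduced.

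**2. Unselective removal of a share d on top of the 3% loss.** n = 40.74 × (1 − d).

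| d | n per arm | Power |
|---|---|---|
| 0 | 40.74 | 80.1% |
| 5% | 38.70 | 78.0% |
| 10% | 36.67 | 75.7% |

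**3. Selective removal: how far the odds ratio could move.** Expected counts at 40.74 per arm are 18.33 with rash and 22.41 without (steroid), and 30.56 with and 10.19 without (control). OR = (18.33/22.41) / (30.56/10.19) = 0.273. It does not move if removal is unrelated to rash within each arm, or equally selective in both arms. Bounds over all ways of removing a few patients:

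- Two removed: 0.219 to 0.299.
- Four removed (about 5% of the 81 followed): 0.166 if all four are controls without rash, (18.33/22.41) / (30.56/6.19); 0.332 if all four are steroid patients without rash, (18.33/18.41) / (30.56/10.19).

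These are worst cases, not estimates. At 0.332 the uncorrected chi-square p-value on the expected counts is about 0.022, against 0.006 with no removal.

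**4. What keeping the patients costs.** Suppose a share f of controls starts a drug with a fraction g of the assumed cream effect. The control rate becomes 0.75 − 0.30 × f × g, with n still 40.74 per arm. At the upper bound g = 1:

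- f = 5%: control rate 0.735, power 75.4%.
- f = 10%: control rate 0.72, power 70.3%.

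Power with everyone kept equals power after unselective removal of the same share at g = 0.465 (f = 5%) or 0.474 (f = 10%). Above that, keeping them costs more power than removing them.

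**The case against.** The strongest reply is that the harmful reading is the one least supported by the text. Section 3.0 links the criteria to registration and gives them no later function. Section 4.7 does not name these starts, and 4.1 and 4.6 set six weeks of follow-up for everyone. The clauses can also be read as screening out patients already expected to start such drugs. All of this stands. A reader might infer that the plan orders these patients to be withdrawn or dropped; it does not. The point is that their place in the analysis is undefined while the eligibility text, read literally, excludes them.

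A second reply is that 9.3 names no analysis set for any patient, so this is one case of a general gap. That is true, but only here does the plan call a randomised patient excluded because of a later event.

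A third is that the effect is small or unknown. At the design rates even the worst case of four removals towards the null leaves p at about 0.022. That also stands, though a result nearer the threshold could be affected.

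Two further inferences go too far. A reader might see a contradiction between 4.1, which foresees antibiotics if an infection develops, and 3.2.2. The 4.1 sentence follows on from cultures taken in the trial, and Table 1 places superinfection of the eruption within grades 3 and 4, which is hard to call another condition. That is at most a matter for clarification. A reader might also conclude that later starts are never captured. The schedule and diary provide no place for them, but the case report forms are not among the documents.

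**Conclusion.** The point holds in a limited form. Two exclusion criteria depend on events after randomisation, and no passage says that patients who meet them are kept in the primary comparison. Harm follows only if the clauses are used to remove patients. Bias in the odds ratio requires in addition that removal depend on both arm and rash. With no rates in the documents, its size and direction are unknown and it may be nil. The power loss of about 2 or 4 points rests on the assumed 5% or 10% and on unselective removal. The gap in the text is certain and its consequence is not. It should be closed because the rule can be settled in wording before data are seen.

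**What to change.** - **3.2.1 and 3.2.2:** apply them only to use within 7 days before registration or use already planned at registration. Keep the chemotherapy-steroid exemption as written. A bare 7-day look-back would go too far, because these criteria would then give no ground for declining a patient known to be about to start such a drug.
- **9.3:** state that a later start does not remove a patient, and that all randomised patients are analysed in the arm assigned in the primary Mantel-Haenszel test, with rash follow-up to week 6 unless consent is withdrawn. The exception is needed because 4.7 permits no follow-up after consent is withdrawn.
- **Weeks 2, 4 and 6:** record any later start (drug, date, reason).
- **Supportive analysis:** label any analysis that leaves these patients out as supportive only, since it is itself open to selection.

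The cost is a wording amendment, one extra entry at three existing visits, and some dilution from concomitant use. That dilution could cost more power than unselective removal: as an upper bound, power falls to about 75% or 70% if 5% or 10% of controls received the full steroid effect. The supportive analysis describes the dilution but does not remove it. No change to clinical management is proposed.

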4.0 TREATMENT PLAN

4.1 Overview

The treatment in this study will include a twice daily application of 0.1% triamcinolone topical cream, applied to the face, chest, and back. In addition, all patients will be instructed to adhere to the same skin treatment regimen, regardless of whether they are in the preemptive or control arm, which will be administered beginning day -3 to day 7(three days before the administration of the first EGFRI dose until 7 days after the administration of the first EGFRI dose) and will be continued through week 6. This regimen will include daily moisturizers as well as use of broad spectrum sun protection before going outdoors.

Patients will be followed every 2 weeks for 6 weeks total, and at each visit will fill out a FACT-EGFRI-18 questionnaire. Optional nasal swab cultures to check for bacterial and fungal growth will be taken at the first and last visit, in addition to any time a culture of the skin is taken. If the patient agrees to the culture and there is bacterial colonization, they will be treated as standard of care. Standard of care is not to treat a positive nasal swab. If an infection develops, this will be treated with antibiotics that cover the bacteria isolated in the culture. In addition, standardized photographs will be taken at each visit, and graded by two blinded dermatologists, if any rash appears. These photos may be used in the future for academic purposes. If they are used outside of the study, the eyes of the participants will be blacked out to help maintain confidentiality. Patients will be given the option to conduct the visits in-person or remotely. If the visit will be conducted remotely, then all required study documentation, diaries, questionnaires, and photography will be submitted to the study team prior to the remote visit for review. For remote visits, the study coordinator will call the subject at the appointment time to review the protocol, answer questions, and review diaries, questionnaires, and AEs.

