While the mechanisms that underlie EGFRI-associated cutaneous toxicities remain incompletely characterized, interference with the follicular and interfollicular EGFR signaling pathway is considered the critical component.³ As EGFRs are primarily expressed in undifferentiated, proliferating keratinocytes in the basal and suprabasal layers of the epidermis and the outer layers of the hair follicle, inhibition of EGFR-mediated signaling pathways alters keratinocyte proliferation, differentiation, migration and attachment, as well as stimulates inflammation, all of which can lead to the distinctive cutaneous manifestations.³

Histologic studies of the EGFRI-induced rash have shown a mixed inflammatory infiltrate within the upper dermis (particularly around hair follicles), follicular rupture, and epithelial acantholysis.³ The lesions are usually sterile, but the eruption can be complicated by secondary bacterial and viral infections in up to 30% of patients; there are even reports of associated bacteremia.^{7,8} The cutaneous toxicity has been graded as moderate to severe in up to 55-60% of patients,^{9,10} and it leads to significant discomfort and pruritus in one-third of patients.⁵ Depending upon severity, up to a third of oncologists will discontinue EGFRI therapy.⁴ In one study, only approximately 8% of providers obtained a dermatology consult to aid in management.⁴

Currently, the EGFRI-induced papulopustular eruption is most commonly assessed utilizing the grading system contained in the National Cancer Institute's Common Terminology Criteria for Adverse Events monograph (NCI-CTCAE; version 4.03) (see Table 1).¹¹

Table 1: NCI-CTCAE, Version 4.03¹¹ Grading for Acneiform Rash

Version Date: 01-25-2021 6

Grade 1	Papules and/or pustules covering <10% BSA, which may or may not be associated with symptoms of pruritus or tenderness
Grade 2	Papules and/or pustules covering 10-30% BSA, which may or may not be associated with symptoms of pruritus or tenderness; associated with psychosocial impact; limiting instrumental ADL
Grade 3	Papules and/or pustules covering >30% BSA, which may or may not be associated with symptoms of pruritus or tenderness; limiting self-care ADL; associated with local superinfection with oral antibiotics indicated

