7.2 Definitions & Descriptions

7.2.1 Adverse Event

An adverse event (AE) is any untoward medical occurrence in a patient receiving study treatment and which does not necessarily have a causal relationship with this treatment. Because AEs associated with EGFR- inhibitor treatment are monitored by the treating oncology physician, for the purposes of this study, only AEs that were possibly, probably, or definitely related to triamcinolone 0.1% cream will be collected, including those symptoms listed in section 8.1.9 will be reported. An AE can therefore be any unfavorable and unintended sign (including an abnormal laboratory finding), symptom, or disease temporally associated with the use of an experimental intervention, whether or not related to the intervention.

Recording of AEs should be done in a concise manner using standard, acceptable medical terms. In general, AEs are not procedures or measurements, but should reflect the reason for the procedure or the diagnosis based on the abnormal measurement. Preexisting conditions that worsen in severity or frequency during the study should also be recorded (a preexisting condition that does not worsen is not an AE). Further, a procedure or surgery is not an AE; rather, the event leading to the procedure or surgery is considered an AE.

If a specific medical diagnosis has been made, that diagnosis or syndrome should be recorded as the AE whenever possible. However, a complete description of the signs, symptoms and investigations which led to the diagnosis should be provided. For example, if clinically significant elevations of liver function tests are known to be secondary to hepatitis, "hepatitis" and not "elevated liver function tests" should be recorded. If the cause is not known, the abnormal test or finding should be recorded as an AE, using appropriate medical terminology (e/g/ thrombocytopenia, peripheral edema, QT prolongation).

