7.3 Adverse Event Reporting

7.3.1 Routine Reporting

All routine adverse events that are determined to be possibly, probably, or definitely related to study treatment should be reported on the adverse event (AE) Case Report Form (CRF) within NOTIS Routine AEs will be reviewed by the Data Monitoring Committee (DMC) according to the study's phase and risk level, as outlined in the DSMP.

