8.1.9 Side effects

- Blistering, burning, crusting, dryness, or flaking of the skin
- Thinning of the skin with easy bruising
- Itching, scaling, severe redness of the skin
- Redness and scaling around the mouth
- Acne or pimples
- Burning and itching of the skin with blisters
- Burning, itching, and pain in hairy areas, or pus at root ofhair
- Increased hair growth on forehead, back, arms, legs
- Lightening of normal skin color
- · Lightening of treated areas of dark skin
- Reddish purple lines on arms, face, legs, trunk, or groin
- Softening of the skin

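### Skin infection is not recorded as a separate outcome comparably in both arms, so the planned adverse-event comparison cannot estimate an infection difference

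*Combined protocol and SAP*

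**What the plan says.** Section 1.1 states that "the eruption can be complicated by secondary bacterial and viral infections in up to 30% of patients". Section 4.1 anticipates infection on study and gives a treatment instruction: "If an infection develops, this will be treated with antibiotics that cover the bacteria isolated in the culture".

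The rules on what is recorded are in Section 7. Section 7.2.1 leaves one class of event outside the study data, because "AEs associated with EGFR- inhibitor treatment are monitored by the treating oncology physician". For the study itself, "only AEs that were possibly, probably, or definitely related to triamcinolone 0.1% cream will be collected". Section 7.3.1 repeats the filter: "All routine adverse events that are determined to be possibly, probably, or definitely related to study treatment should be reported". The expected side effects in Section 8.1.9 contain no infection term; the nearest is "Burning, itching, and pain in hairy areas, or pus at root ofhair".

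Section 9.3 then compares adverse-event incidence between arms with Fisher's exact test. Infection is not among the endpoints in Sections 2 and 6, the rows of the Section 5 schedule or the analyses in 9.3. The only culture objective (2.2.4, 6.3.4) relates the optional baseline nasal swab to rash.

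Three routes do let infection into the data:
- a non-serious infection judged at least possibly related to the cream is an adverse event;
- a serious infection is an SAE whatever its attribution (7.2.3);
- superinfection is one of the descriptors of rash grades 3 and 4 in Table 1, and maximum grade is compared by arm (9.3).

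**The concern.** The trial applies a steroid for six weeks to skin that the protocol itself describes as prone to infection. Whether infection goes up (a cost of the steroid) or down (a benefit of less eruption) is a natural safety question. To answer it, infection must be ascertained in the same way in both arms.

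The attribution filter prevents that. Relatedness to a cream can be judged only in someone who uses it, so the filter works differently in the two arms. The resulting comparison could miss a real difference. It could also show an excess in the steroid arm where none exists.

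**Working it through.** **1. The plan's own figure.** Section 9.2 gives 45% against 75%, 80% power and 42 per arm; the Study Summary gives a two-sided 5% level. With the pooled normal approximation and no continuity correction:

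n = [1.96·√(2·0.60·0.40) + 0.842·√(0.75·0.25 + 0.45·0.55)]² / 0.30² = (1.358 + 0.555)² / 0.09 ≈ 40.7, so 41 per arm (82 in total).

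Power is 79.3% at 40 per arm and 81.3% at 42. Allowing for 3% loss, 80 / 0.97 = 82.5, so 83, or 84 when made even. The stated size reproduces. It concerns rash; the plan gives no figure for infection.

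**2. How many infections might be at issue.** The 30% in Section 1.1 is an upper figure. It covers bacterial and viral infection, has no six-week window, and its denominator is unclear.
- If it applies to all randomised patients: 0.30 × 42 = 12.6 per arm.
- If it applies to patients with eruption, at the Section 9.2 rates: control 0.30 × 0.75 × 42 = 9.5; steroid 0.30 × 0.45 × 42 = 5.7.

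The second line takes the 9.2 rates as the proportion with any eruption. Section 9.2 calls them rash incidence without stating a grade.

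**3. What the attribution filter does.** Assume a true infection rate of 30% in both arms, 40 evaluable per arm, and no recorded infection in control because those patients are not on the cream. With 0 of 40 in control, the two-sided Fisher p-value is 2·C(40,6)/C(80,6) = 0.026 for 6 steroid-arm events and 2·C(40,5)/C(80,5) = 0.055 for 5. Significance therefore needs at least 6 recorded events.

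| Share of steroid-arm infections attributed to cream (assumed) | Expected recorded, steroid vs control | Chance of p ≤ 0.05 with no true difference |
|---|---|---|
| 25% | 3 vs 0 | 8% |
| 50% | 6 vs 0 | 57% |
| 100% | 12 vs 0 | 99% |

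If nothing is attributed, the comparison shows nothing. The result depends on the attribution habit rather than on the infection rate. The zero in control is the limiting case: under Section 4.5 a control patient with rash may be given triamcinolone, and could then have a cream-related event.

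**4. What equal recording would give.** Half-width of the 95% CI for the difference at equal rates = 1.96·√(2p(1−p)/n).

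| p | n = 42 per arm | n = 40 per arm |
|---|---|---|
| 30% | 19.6 points | 20.1 points |
| 20% | 17.1 points | 17.5 points |
| 10% | 12.8 points | 13.1 points |

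The 20% and 10% rates are assumptions. At 40 per arm, power for 30% against 15% is 36% by the normal approximation and 28% by Fisher's test. From 30%, 80% power (normal approximation) needs a rise to about 61% or a fall to about 6%. Detecting 30% against 15% with 80% power would need 121 per arm.

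**The case against.** A reader might infer that infection is not collected at all, or that almost all non-serious infections go unrecorded. The documents do not support either. The threshold for an adverse event is only a possible relation to the cream, which many assessors would accept for an infection on steroid-treated skin. The Section 8.1.9 list is not a closed filter, since 7.2.1 presents it as included among the collected events. SAEs are taken regardless of attribution. No source in the documents gives the share that would be missed.

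A reader might also infer that a lower rash grade with more infection would pass as a clean success. Table 1 limits that. If the superinfection descriptor is enough for grade 3, an infected eruption for which oral antibiotics are indicated raises the grade and counts against the steroid in the grade 2 or greater endpoint.

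These points stand, and they narrow the gap without closing it. The adverse-event route remains one-sided. SAEs cover only serious infections. Grade 3 combines superinfection with more than 30% of body surface and self-care limitation, so a grade cannot be turned back into an infection count. An infection that is not serious, not attributed to the cream and not graded as superinfection is lost.

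It is also fair to say that a separate infection outcome in an 84-patient phase II trial is partly a matter of choice, and that equal recording would not isolate the steroid. Control patients with rash may receive triamcinolone, antibiotics or both (4.5). Both limits apply to how the result should be read; neither is a reason to keep an attribution-dependent comparison.

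**Conclusion.** The point holds in this form: skin infection has no separate, comparable record in the two arms, and the planned Fisher comparison cannot estimate an infection difference in either direction. This follows from Sections 7.2.1, 7.3.1 and 9.3 and does not depend on any assumed rate.

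The size does depend on assumptions. At most 12 to 13 infections per arm are at issue if the 30% applies to everyone randomised, and about 9 control and 6 steroid if it applies to patients with rash at the 9.2 rates. Both are upper figures, and some of these infections would be captured by the three existing routes. The false-positive figures rest on an assumed 30% rate in both arms and on assumed attribution shares; they show the mechanism and do not predict what will happen. The gap affects the safety interpretation, not the validity of the randomised rash comparison.

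**What to change.** At the existing week 2, 4 and 6 adverse-event review in Section 5, record for every randomised patient, regardless of attribution, any clinically diagnosed or culture-positive skin infection on the face, chest or back since the last visit. Include the date, the organism if cultured, and the date of any antibiotic start. Exempt this item from the attribution filter in 7.2.1 and 7.3.1. In Section 9.3, report the proportion by arm with a risk difference and 95% CI, labelled as a descriptive safety outcome and kept separate from rash grade.

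The cost is one CRF item and one table. No extra visit is needed, since skin examination, photographs and side-effect review are already scheduled at those weeks, and no extra culture is needed. Three limits remain:
- the interval will be wide, as shown in the working;
- diagnosis will be less certain at remote visits, which rely on a telephone call and submitted photographs (4.1, 4.6), so the CRF should define what counts as an infection and who decides;
- because of Section 4.5, the result compares treatment strategies, not steroid against no steroid, and should be described that way.
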